4.4 WITHDRAWAL CRITERIA

Patients who are removed from the study treatment due to adverse experiences (clinical or laboratory) will be treated and followed according to accepted medical practice. All pertinent information concerning the outcome of such treatment must be recorded in the CRF.

Patients who withdraw their consent from participating in the trial will be withdrawn from protocol procedures. Data that has been collected on these patients to this timepoint will be included in the analyses.

The discontinuation of study treatment will occur under the following circumstances

- Unacceptable toxicity
- Any patient who experiences a WHO CTC grade 3 adverse reaction (AR), possibly or likely to be related to vaccination will discontinue further vaccination.
- Severe local toxicity (CTC 3 or greater) at the site of injection, development of clinically relevant anti-DNA antibodies or rheumatoid factors, clinical or biochemical evidence of muscle destruction (CTC 3 or greater) or other unexpected toxicity will lead to termination of the vaccination of that patient.

- Unforeseen events: any event which in the judgement of the Investigator makes further treatment inadvisable
- SAE requiring discontinuation of treatment
- The patient withdraws consent where a patient is not evaluable, additional patients will be recruited to replace them (See Section 3.1)
- Serious violation of the study protocol (including persistent patient attendance failure and persistent non-compliance)
- Evidence of disease progression
- In patients with CML requirement to discontinue or change the dose of tyrosine kinase inhibitor therapy

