5.4 DOSE MODIFICATIONS, REDUCTIONS AND DOSE DELAYS

There will be no dose reductions or dose modifications.

Haematological toxicity – If patients experience CTC toxicity >2, vaccination will not be administered. Further vaccination may be offered after normalization if appropriate in the opinion of the treating clinician and only after documented discussion with the UoSCTU and lead investigators. Severe local toxicity (CTC 3 or greater) at the site of injection, development of clinically relevant anti-DNA antibodies or rheumatoid factors, clinical or biochemical evidence of muscle destruction (CTC 3 or greater) or other unexpected toxicity will lead to termination of the vaccination of that patient.

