7.1.8 OTHER SYSTEMIC TOXICITY

Haematological toxicity: It is possible that vaccination with WT1 may cause cytopaenias in patients who have a hypocellular low marrow reserve (hypocellular bone marrow). This is because WT1 is also expressed at low levels in normal CD34+ stem cells. To minimise the possibility of this, we will exclude patients with low marrow reserve (bone marrow cellularity <20%). Patients who develop cytopaenia will be treated with 5 days of intravenous methylprednisone (1-2 mg/kg). This steroid treatment will not start for 2-3 weeks after the start of cytopaenia to allow time to determine if cell counts rebound. They will also be given supportive care including blood products, growth factors and antibiotics as clinically indicated until the counts recover. The development of other systemic toxicity appears unlikely. FBC, biochemistry, in particular renal function and clinical AE will be assessed by CTC criteria.

• If CTC toxicity >2 occurs in a particular patient, vaccination will be paused. Further vaccination may be offered after normalization if appropriate in the opinion of the treating clinician and only after documented discussion with the UoSCTU and lead investigators.

Cardiac or renal toxicity: It is possible but from the available dataset in the literature unlikely, that the patients may develop immune related toxicity that affects the kidney or cardiac function. Patients will therefore have regular monitoring of their renal function, including urine sampling for proteinuria, and an ECG before any vaccination dose is given. Additional tests will be undertaken as clinically indicated, should signs of renal or cardiac dysfunction occur.

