8 PHARMACOVIGILANCE

8.1 **DEFINITIONS**

The Medicines for Human Use (Clinical Trials) Regulations 2004, as amended, provides the following definitions relating to adverse events in trials with an investigational medicinal product:

Adverse Event (AE): any untoward medical occurrence in a patient or clinical trial subject administered a medicinal product and which does not necessarily have a causal relationship with this treatment. *An AE can therefore be any unfavourable and unintended sign (including an abnormal laboratory finding), symptom, or disease temporally associated with the use of an investigational medicinal product (IMP), whether or not considered related to the IMP.*

Adverse Reaction (AR): all untoward and unintended responses to an IMP related to any dose administered.

All AEs judged by either the reporting investigator or the sponsor as having reasonable causal relationship to a medicinal product qualify as adverse reactions. The expression reasonable causal relationship means to convey in general that there is evidence or argument to suggest a causal relationship.

Unexpected Adverse Reaction: an AR, the nature or severity of which is not consistent with the applicable product information (e.g. investigator's brochure (IB) for an unapproved investigational product).

When the outcome of the adverse reaction is not consistent with the applicable product information this adverse reaction should be considered as unexpected. Side effects documented in the IB which occur in a more severe form than anticipated are also considered to be unexpected.

Serious Adverse Event (SAE) or Serious Adverse Reaction (SAR): any untoward medical occurrence or effect that at any dose:

- Results in death
- Is life-threatening refers to an event in which the subject was at risk of death at the time of the event; it does not refer to an event which hypothetically might have caused death if it were more severe
- Requires hospitalisation, or prolongation of existing inpatients' hospitalisation
- Results in persistent or significant disability or incapacity
- Is a congenital anomaly or birth defect

Medical judgement should be exercised in deciding whether an AE/AR is serious in other situations. Important AE/ARs that are not immediately life-threatening or do not result in death or hospitalisation but may jeopardise the subject or may require intervention to prevent one of the other outcomes listed in the definition above, should also be considered serious.

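### Sections 4.4, 5.4 and 7.1.8 give incompatible instructions for the same toxicity above grade 2 (permanent stop or pause with restart), and the unexpected-toxicity item has no stated scope

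*Protocol*

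**What the plan says.** Three sections of the protocol tell a site what to do when a vaccinated patient has toxicity.

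- **Section 4.4 (withdrawal criteria)** has three relevant entries. One ends vaccination for a grade 3 adverse reaction judged possibly or likely due to the vaccine. One lists severe local, antibody and muscle findings and closes with "other unexpected toxicity will lead to termination of the vaccination of that patient". One is discretionary: "Unforeseen events: any event which in the judgement of the Investigator makes further treatment inadvisable". None of them provides for restart.
- **Section 5.4 (dose modifications and delays)** opens with a rule labelled haematological: "If patients experience CTC toxicity >2, vaccination will not be administered". Restart is then possible after recovery and a documented discussion. The same paragraph goes on to the termination sentence also found in 4.4. It begins "Severe local toxicity (CTC 3 or greater) at the site of injection, development of clinically relevant anti-DNA antibodies or rheumatoid factors", adds muscle destruction at CTC 3 or greater, and ends "or other unexpected toxicity will lead to termination of the vaccination of that patient".
- **Section 7.1.8 (other systemic toxicity)** states: "If CTC toxicity >2 occurs in a particular patient, vaccination will be paused". It continues: "Further vaccination may be offered after normalization if appropriate in the opinion of the treating clinician", again after a documented discussion.

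Section 8.1 defines an unexpected adverse reaction as "an AR, the nature or severity of which is not consistent with the applicable product information". That definition has no minimum grade.

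**The concern.** A stopping rule has to give one answer for one event. Here a site that consults 4.4 and a site that consults 5.4 or 7.1.8 can reach opposite answers for the same patient: one ends vaccination for good, the other waits and may resume. This matters for safety, because these events are what the rules exist to control.

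It also bears on the analysis. Section 5.2 plans 6 four-weekly and 6 three-monthly vaccinations, 12 in all. Section 10.2 keeps patients in the molecular analysis after a single dose if two post-baseline samples exist, and applies intention to treat to the analyses not given their own population, which include AML progression-free survival. A patient whose vaccination is ended early can therefore still count towards the 32 CML or 39 AML patients on whom the decision rules rest. How much vaccine those patients received would depend in part on which section was followed.

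**Working it through.** No arithmetic applies, and the plan gives no figure to reproduce. The check is to take each kind of event through every rule that could reach it. CTC >2 means grade 3 or higher, so the rules meet at grade 3.

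| Event | 4.4, related grade 3 entry | Termination sentence (4.4 and 5.4) | 5.4, haematological rule | 7.1.8 rule |
|---|---|---|---|---|
| Grade 3 haematological, related, listed in the Investigator's Brochure | Discontinue | Not triggered | Withhold, may restart | Pause, may restart |
| Grade 3 haematological, related, unlisted | Discontinue | Terminate | Withhold, may restart | Pause, may restart |
| Grade 3 other systemic, related, listed | Discontinue | Not triggered | Does not apply | Pause, may restart |
| Grade 3 other systemic, related, unlisted | Discontinue | Terminate | Does not apply | Pause, may restart |
| Grade 1–2 systemic, unlisted | Not triggered | Terminate if read literally; unclear otherwise | Not triggered | Not triggered |

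**Rows 1 and 2.** The conflict here does not depend on interpretation. 4.4 ends vaccination for a related grade 3 reaction. 5.4 withholds it for haematological toxicity of that grade and lets it resume, with no condition on relatedness. In row 2 the conflict also lies within 5.4, where the two instructions share one paragraph.

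**Rows 3 and 4.** The conflict depends on the reach of the 7.1.8 rule. The section is headed for other systemic toxicity. The sentence before the rule covers blood count, biochemistry, renal function and clinical adverse events, and the rule itself names no organ system. The natural reading is that it covers systemic toxicity generally.

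**Row 5.** This is an ambiguity, not a contradiction. Local toxicity and muscle destruction carry a grade in the termination sentence; the unexpected-toxicity item carries neither a grade nor any other limit. If a site borrows the 8.1 definition, a mild reaction missing from the product information qualifies. 7.1.8 takes no action on such an event, because its trigger lies above grade 2.

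**The case against.** Four arguments have some force.

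1. **The rules could be meant for different events.** The 7.1.8 rule follows a paragraph on haematological toxicity and matches the rule that 5.4 labels haematological. Pausing could then be for blood counts, and termination for local, autoimmune, muscle and other findings. This would ease rows 3 and 4. It does not ease row 1, because the related grade 3 entry in 4.4 makes no exception for haematological reactions.
2. **Pausing could be meant for unrelated toxicity.** 4.4 is conditional on relatedness, and 5.4 and 7.1.8 are not. But 7.1.8 starts from the possibility that WT1 vaccination itself causes cytopenias, so its rule cannot be confined to unrelated events.
3. **The unexpected-toxicity item closes a list of serious findings**, so it could mean toxicity of similar seriousness. That is a fair reading. A reader might instead infer that the protocol ends vaccination for unexpected toxicity of any grade. The text does not say so; that inference comes from silence and from a pharmacovigilance definition not written for dosing. If 8.1 is carried over, it also brings relatedness with it, since an adverse reaction is by definition related to the product. What stands is that the scope is unstated and two careful readers can differ.
4. **The discretionary entry in 4.4 does not contradict 5.4.** A reader might set the two against each other. In fact 4.4 carries the same termination sentence as 5.4, and the entry on unforeseen events is only a further ground for stopping. It gives no discretion to continue when another entry applies. This objection stands in full.

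**Conclusion.** The contradiction is firm at grade 3. A haematological reaction of that grade that is related to vaccination ends vaccination under 4.4 and only interrupts it under 5.4. The same conflict arises with 7.1.8, and extends to other systemic toxicity if that section is read as its heading suggests. An unexpected haematological or systemic event above grade 2 meets the same clash through the termination sentence. The missing scope of the unexpected-toxicity item is a secondary ambiguity.

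Two stronger conclusions are tempting and unsupported. One is that a mild unlisted event is treated more severely than a grade 3 systemic one. That looks only at 7.1.8 and overlooks 4.4, which discontinues vaccination for a related grade 3 reaction. The other is that the wording costs the trial a stated amount of power. The protocol gives no rate of unlisted reactions and no basis for assuming that patients stopped early respond at the null rate. What counts as unlisted depends on an Investigator's Brochure that is not at hand. No size can therefore be put on lost doses or lost power. Divergence between sites is a likely consequence of the wording, but it is an inference.

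The point should be corrected because it concerns patient safety and is cheap to settle.

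**What to change.** Reconcile 4.4, 5.4 and 7.1.8 so that the same event leads to the same action wherever a site looks. In particular, settle whether a related or unexpected haematological or systemic event above grade 2 ends vaccination or interrupts it, and say which toxicities the 7.1.8 rule covers. State the scope of the unexpected-toxicity item in identical words in 4.4 and 5.4, including whether the 8.1 definition applies to it. The choice of clinical rule, and whether scope is set by grade or in some other way, belongs to the sponsor and investigators.

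The cost is a wording change in three sections, with the amendment review that section 11.3 requires. It needs no additional patients, visits or data.

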5.5 DOSE ESCALATION

There will be no dose escalation

5.6 CONCURRENT MEDICATION AND REPLACEMENT

Systemic steroids or other drugs with a likely effect on immune competence are forbidden during the trial. The predictable need of their use will preclude the patient from trial entry. Inhaled steroids are allowed. Concomitant medication may be given as medically indicated.

Patients with CML-CP will continue on tyrosine kinase inhibitor therapy and the dose of tyrosine kinase inhibitor therapy will remain unchanged throughout the course of the study. Patients will continue on the same dose of tyrosine kinase inhibitor therapy as prior to enrolment. Details of the concomitant medication given must be recorded in the Case Report Form (CRF).

The patient must not receive other anti-cancer therapy or investigational drugs while on study.

6 PHARMACEUTICAL INFORMATION

6.1 SUPPLY OF VACCINE

The DNA vaccine construct has been prepared and sequenced in the Department of Molecular Immunology, Cancer Sciences Division, University of Southampton.

The bulk preparation and sterile fill will be performed in accordance with Good Manufacturing Practice (GMP) at the MHRA approved laboratory at the Clinical Biotechnology Centre, Bristol. This facility has also received approval for vaccine preparation by the FDA and conforms to GMP standards according to the new European guidelines. The vaccine will comply with stringent Quality Control (QC) criteria, as for our previous trials. Vaccine batches will be controlled for sterility, purity, endotoxin level and by restriction enzyme digest and nucleotide sequencing before release for clinical use.

A complete certificate of analysis will be provided with each batch of vaccine and will be retained in the trial Investigator's File/ Pharmacy File.

For information on the vaccine contact either the Coordinating Investigator or:

[name]

Clinical Biotechnology Centre Bristol Institute for Transfusion Science Work address [name] [contact] E-mail address [contact]

A copy of the drug shipment form will be sent to the MHRA by the supplier.

6.2 PHARMACEUTICAL DATA

6.2.1 STUDY AGENT FORMULATION

The concentration of DNA will be 1mg/dose for p.DOM-WT1-37 and 1mg/dose for p.DOM-WT1-126 (*at a final concentration of 1 mg/0.8mL*). The vaccine is supplied in standard Phosphate Buffer Solution (PBS). The DNA for injection will be divided into aliquots for storage at -70° C in sterile glass vials and aliquots for sterility and stability testing. The testing will be based on the guidelines for injectables described in the European Pharmacopoeia. The most likely contaminant is protein, this is expected to be <1%. The material will be confirmed as pyrogen free by using a limulus test (Bio Whittaker (UK) Ltd). After delivery to the Hospital Pharmacy the vaccine will be stored at -70° C.

6.2.2 STORAGE CONDITIONS & STABILITY OF UN-RECONSTITUTED INVESTIGATIONAL DRUG FORMULATION

The vaccine must be stored -70°C or below. Before thawing, the vaccine is stable for at least 2 years @ - 70°C, based on our previous experience with DNA fusion vaccine plasmids produced in Bristol.

6.2.3 METHOD OF RECONSTITUTION

The vaccine should be thawed for approximately 5 minutes before injection at room temperature, and is stable for 24hrs. Shaking is not necessary.

6.2.4 STABILITY AFTER RECONSTITUTION AND LABELLING

The thawed vaccine must be used within 24 hours.

Labelling requirements for the vaccine Amount and Name of Vaccine Total volume Concentration Date of preparation Expiry date and time

6.3 ELECTROPORATION DEVICE

The Elgen1000 is an electroporation system specifically designed for the delivery of electrical pulses to selected tissues including muscle to facilitate the intracellular uptake of plasmid DNA. The device locally applies controlled, short duration electric pulses to target tissues to create an electric field which temporarily increases cellular membrane permeability allowing the plasmid DNA to enter the cells.

The Elgen1000 consists of an electrical pulse generator (Control Unit) and an automated injector unit for delivery of drug (DNA) and electrical pulses. Upon user activation the disposable needles mounted in the Injector Unit advances into the muscle at the same time as the DNA is injected. Upon user activation, when the insertion/injection comes to an end, the Control Unit to deliver a sequence of electric pulses to the needle electrodes on the Injector Unit. The resulting electrical field at the treatment site produces the required environment to enhance cell membrane permeability allowing DNA to efficiently enter the cell interior.

The Control Unit is a durable medical electronic apparatus that provides series of short duration, moderate voltage electric pulses. Treatment protocols defining electrical pulsing patterns as well as injection volumes and electrode insertion depth can be pre-programmed on an onboard flash card. Patient data and treatment records can also be stored in the flash card memory. For the proposed trial a pulse sequence of 2 pulses of 60ms pulses at 400 mA will be used. Studies in rhesus macaques shows that

these parameters give an electrical field of approximately 125V/cm using two parallel needle electrodes 4mm apart and inserted approximately 15 mm into the tissue.

The unit connects to line voltage and consists of a medical grade power supply unit (PSU), high-voltage power circuit and a low-voltage digital control circuit. The PSU provides patient / user electrical isolation and converts local line power to the voltage required by the instrument. The control circuit consists of a standard microprocessor-based controller board for the user interface, and a separate and insulated embedded microprocessor for the real time hardware interface. The high voltage is generated by a series of DC-DC converters on the power circuit board and the voltage is discharged and regulated through a power transistor. An array of power transistors is used to route the sequence of pulses to the needles, as well as to control the polarity of pulses.

The Injector Unit is an automated two motor device; one electrical motor drives a movable carriage where a sterile lid containing two disposable syringes with needles are mounted. The second motor operates the pistons of the syringes for the injection of DNA. Needle insertion depth (0-20 mm), and injection volume (20-600 ul) are programmed in the control unit. After the treatment, the lid containing syringes and needles will be disposed of along with a single use injector tip. The needles are connected to the Control Unit through insulated wires, which run through the Injector Unit handle and terminates in an integrated connector. An insulated cable, reaching 6.5 feet, connects Injector and Control Units. The connector attaches to the front panel of the Elgen 1000 Control Unit.

The DNA filled syringes with needles are positioned in a disposable lid and mounted on the top of the Injector Unit. The lids are manufactured to accommodate 22 Gauge needles. The distance between the needles electrodes are 4 mm.

Control Unit

Injection Unit with lid and syringes containing the vaccine The Elgen1000 electroporation device

6.3.1 TRAINING AND EXPERIENCE REQUIRED

The investigation will be performed under the supervision of a trained and experienced physician. The operator will be competent in the use of all parts of the device and be able to identify the proper area to be injected. The operator will have undergone formal training and be familiar with:

The instructions for use

Handling of the injection device (mounting the standard syringes and needles) Operation of the electroporator

Training will be provided by INOVIO BC, San Diego and/or by the clinical trials team from Southampton.

6.4 VACCINE ADMINISTRATION

6.4.1 DNA VACCINATION WITH ELECTROPORATION

The two syringes with two parallel needles, 4 mm apart, will be filled with DNA and mounted in the Injection unit. The front of the Injector will be placed against the skin of the patient and insertion of the needles initiated. At approximately 5mm tissue depth, injection of the DNA starts automatically during further insertion (15-20 mm). A total of 400 ul DNA will be injected. Immediately after injection and insertion has stopped, electrical pulses are delivered to the tissue using the injection needles as electrodes. When the stimulation has ended, the needles are automatically withdrawn. For each treatment 2 unipolar pulses of 60 ms at 200 ms interval using a current of 400mA (approximately 125V/cm) will be applied. The procedure from needle insertion to needle withdrawal will take approximately 5 seconds.

Painkillers (eg. paracetamol) will be provided. Of note, this was not necessary for any patient in the study GTAC 089.

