Dosage Regimen / Duration of Treatment:	p.DOM-WT1-37: 1mg/dose/vaccine and p.DOM-WT1-126: 1mg/dose/vaccine The DNA vaccine will be administered 12 times. In the first 6 months patients will receive the vaccine at 4 weekly intervals into separate sites. After this vaccinations will be administered every 3 months to a maximum of 24 months. Vaccines will be injected intramuscularly and followed by intramuscular electroporation.
Concomitant Therapy:	Steroids or other drugs with a likely effect on immune competence are not permitted during the course of the trial. Concomitant medication may be given as medically indicated. Patients with CML-CP will continue on tyrosine kinase inhibitor therapy.

REFERENCE DIAGRAM

	baseline	w0	w2	w4	w8	W10	w12	w16	w20	w22	w24- w28	w32	w34	m11 d0	m14 d0	m17 d0	m17 d14	m20 d0	m23 d0	m24 d0	m27	m30	m33	m36 EOT
Visit number	0	1	2	3	4	5	6	7	8	9	10	11	12	13	14	15	16	17	18	19	20	21	22	23
Informed consent	*																							
HLA status																								
Expression of WT1	*																							
in tumour cells																								
Demographic Data	*																							
Medical history/	*																							
Malignancy																								
Prior Treatment	*																							
Malignancy																								
Height & Weight	*	*	*	*	*		*	*	*			*		*	*	*		*	*		*	*	*	*
Physical	*	*	*	*	*		*	*	*			*		*	*	*		*	*		*	*	*	*
examination	*	÷	-1-		Ť				÷			Ŧ		*	Ť			-1-	Ŧ		-1-	4	Ŧ	*
WHO																								
Performance	*	*	*	*	*		*	*	*			*		*	*	*		*	*		*	*	*	*
Status																								
Vital signs	*	*	*	*	*		*	*	*			*		*	*	*		*	*		*	*	*	*
Assessment of																								
pain/ discomfort	*	*		*	*		*	*	*			*		*	*	*		*	*					
and distress																								
ECG Echocardiogram	* Echo at baseline only unless clinically indicated	*(1)		*	*		*	*	*			*		*	*	*		*	*					
FBC and																								
differential blood	*	*	*	*	*	*	*	*	*	*	*	*	*	*	*	*	*	*	*	*	*	*	*	*
count, ESR	*																							*
Clotting	*																							*
Biochemistry including CK Urine test for proteinuria	*	*	*	*	*	*	*	*	*	*	*	*	*	*	*	*	*	*	*	*	*	*	*	*
Syphilis, Hep B, Hep C, HIV, EBV, CMV	*																							
Immunological	*	*	*	*	*	*	*	*	*	*	*	*	*	*	*	*	*	*	*	*	*	*	*	* 70ml
monitoring (2)	80ml	70ml	70ml	70ml	70ml	70ml	70ml	70ml	70ml	70ml	70ml	70ml	70ml	70ml	· /umi									
qPCR for BCR- ABL/WT	*	*	*	*	*	*	*	*	*	*	*	*	*	*	*	*	*	*	*	*	*	*	*	*

SCHEDULE OF OBSERVATIONS AND PROCEDURES FOR HLA A2 POSITIVE PARTICIPANTS

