5.1 VACCINE DOSE

p.DOM-WT1-37: 1mg/dose/vaccine p.DOM-WT1-126: 1mg/dose/vaccine

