5.3 VACCINE ROUTE AND SITE

The vaccines will be injected by deep intramuscular injection (IM) followed by electroporation (EP) by a trained health care professional. The vaccines will not be mixed but will be administered into separate sites.

Refer to Section 6.4 for vaccine administration details.

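### Protocol 6.4.1 describes one two-syringe application totalling 400 µl, which holds 0.5 mg at the stated concentration; the prescribed 1 mg per vaccine needs 800 µl, and the protocol does not say how that volume is made up.

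*Protocol*

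**What the plan says.** The dose is stated consistently. The synopsis gives "p.DOM-WT1-37: 1mg/dose/vaccine and p.DOM-WT1-126: 1mg/dose/vaccine", 5.1 repeats it ("p.DOM-WT1-37: 1mg/dose/vaccine", and the same for the second vaccine), and 6.2.1 gives 1 mg per dose for each vaccine, "at a final concentration of 1 mg/0.8mL". Section 5.4 allows no dose reduction or modification. Section 5.3 keeps the two vaccines unmixed and in separate sites, then says "Refer to Section 6.4 for vaccine administration details".

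Section 6.4.1 is that administration text. It describes two syringes with parallel needles mounted in one injector, a single insertion during which the DNA is delivered, one pulse sequence, and automatic withdrawal. On volume it says "A total of 400 ul DNA will be injected". On the pulses it says "For each treatment 2 unipolar pulses of 60 ms at 200 ms interval", and on duration "The procedure from needle insertion to needle withdrawal will take approximately 5 seconds".

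Section 6.3 describes the device and says "injection volume (20-600 ul) are programmed in the control unit". It does not say whether that range applies to each syringe or to both together.

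**The concern.** A reader who follows 6.4.1 for each vaccine, carrying out the one procedure it describes at the volume it states, gives half of the only dose the protocol permits. The text that would close the gap, either a second application per vaccine or a volume per syringe, is not in the protocol.

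Two practical matters depend on it. One is that the operative instruction should deliver the prescribed dose in a trial with a single dose level. The other is patient burden: the number of electroporations per visit is 2 or 4, depending on how the volume is made up. Section 1.8.3 reports electroporation as painful, although the pain resolved within minutes in earlier patients, and pain immediately after vaccination and at 48 hours are secondary endpoints in 2.2. A reader of the protocol cannot tell how many applications a pain score would reflect.

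**Working it through.** **Inputs**
- Dose per vaccine per vaccination: 1 mg (synopsis, 5.1, 6.2.1).
- Concentration: 1 mg per 0.8 mL (6.2.1), so 1 / 0.8 = 1.25 mg/mL.
- Volume in the procedure described: 400 µl in total, from two syringes (6.4.1).
- Device range: 20-600 µl, basis not stated (6.3).
- Vaccinations per patient: 12 (synopsis; 6 + 6 in 5.2).

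**Volume needed for the stated dose**

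Volume = dose / concentration = 1 mg / 1.25 mg/mL = 0.8 mL = 800 µl per vaccine, or 1600 µl per visit for both vaccines.

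**Dose in the volume stated in 6.4.1**

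Dose = volume × concentration = 0.4 mL × 1.25 mg/mL = 0.5 mg, which is 50% of 1 mg. For 400 µl to hold 1 mg, the concentration would have to be 1 / 0.4 = 2.5 mg/mL, twice the stated value.

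**Ways to reach 1 mg**

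| Reading | Volume per vaccine | Dose per vaccine | Electroporations per visit | Over 12 vaccinations |
|---|---|---|---|---|
| One application, 400 µl in total (as described) | 400 µl | 0.5 mg | 2 | 24 |
| Two applications of 400 µl | 800 µl | 1.0 mg | 4 | 48 |
| One application, 400 µl from each of two syringes | 800 µl | 1.0 mg | 2 | 24 |

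The second row keeps every number in the protocol but adds an application that is stated nowhere. The third row keeps the single application but conflicts with the word *total* in 6.4.1.

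**Does the device range decide between them?**
- If 600 µl is the maximum for both syringes together, one application gives at most 0.6 × 1.25 = 0.75 mg, and two applications are needed.
- If 600 µl is the maximum per syringe, 400 µl in each of two syringes fits in one application.

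Section 6.3 does not say which, so the range does not settle the question.

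**Other text that might fill the gap**
- The 12 vaccinations count dosing occasions, not applications within an occasion.
- The separate sites in 5.3 keep the two vaccines apart; they do not split one vaccine.

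**The case against.** The strongest reply is that this is an omission, not a wrong figure. Section 6.4.1 describes one cycle of the device, gives no dose in mg, and does not say that one cycle is a whole dose. Two 400 µl cycles make exactly 0.8 mL, which fits a split dose. Several applications in one session are not foreign to the protocol: 1.8.3 describes up to four saline applications per volunteer, each into a separate site. Much of this stands. A reader might infer that the text cannot be reconciled with 1 mg. That goes too far, because two applications per vaccine would reconcile every stated number. What remains is that no section gives that instruction, and the only procedure described falls short by half.

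A reader might also infer that the intended dose is itself unclear, 0.5 mg or 1 mg. The documents do not support this. The dose is 1 mg in three places, no dose modification is allowed, and 0.5 mg appears nowhere. What is open is how the 800 µl is delivered.

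There are also safeguards. The label carries amount, total volume and concentration (6.2.4), injection volumes can be pre-programmed (6.3), and operators are formally trained and familiar with the instructions for use (6.3.1), which are not at hand and may give the split. These make an actual dosing error less likely, but they do not correct the sentence.

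Finally, loss of activity at 0.5 mg is not shown. Section 1.3 reports no dose response between 500 and 2500 µg for a different DNA vaccine, and 400 µg with electroporation was a dose level in the prostate study.

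**Conclusion.** The point holds as an error in the administration text. As written, the one procedure in 6.4.1 delivers 0.5 mg against a prescribed 1 mg per vaccine, a factor of two. The 0.5 mg figure assumes the concentration in 6.2.1 is correct, takes 400 µl as the total for both syringes, and assumes one application per vaccine. The first two follow the protocol's wording; the third is the only procedure it describes, though it never says that one application is the full dose.

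It is probably a drafting error. A reader might infer that patients were under-dosed, or that dose varied between patients or sites, and might multiply the shortfall over 12 vaccinations. Nothing in the protocol supports that, because it does not show how the vaccine was actually given. Sample size, error rates and analyses are unaffected. It should be fixed because the sentence concerns the trial's only dose level and the number of electroporations per visit, and the correction is small.

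**What to change.** Amend 6.4.1 to state the volume per syringe and the number of applications per vaccine, so that together they total 0.8 mL (1 mg) per vaccine. Use whichever was intended:
- two applications of 400 µl in total per vaccine, which makes 4 electroporations per visit; or
- one application with 400 µl from each of the two syringes, which makes 2 per visit.

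State whether the 20-600 µl range in 6.3 is per syringe or per application, and confirm that the chosen volume fits. Leave the concentration in 6.2.1 alone unless it is confirmed to be a typing error; an actual change in fill concentration would be a product change and is not proposed.

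The cost is one or two sentences, plus the amendment route in 11.3 (approval by the Chief Investigator, review by GTAC and the MHRA). It needs no extra patients or visits and no change to the analysis.
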